Part	A single component of a study that contains different objectives or populations within that single study. Common parts within a study are a single dose part and a multiple dose part, or a part in patients with established disease and in those with newly diagnosed disease.
Patient	An individual with the condition of interest
Personal data	Subject information collected by the Investigator that is transferred to Novartis for the purpose of the clinical trial. This data includes subject identifier information, study information and biological samples.
Randomization number	A unique identifier assigned to each randomized subject, corresponding to a specific treatment arm assignment

Run in Failure	A subject who is screened but not randomized/treated after the run-in period (where run-in period requires adjustment to subject's medications or other intervention)
Screen Failure	A subject who is screened but is not treated or randomized
Source Data/Document	Source data refers to the initial record, document, or primary location from where data comes. The data source can be a database, a dataset, a spreadsheet or even hard-coded data, such as paper or eSource
Study treatment	Any drug or combination of drugs administered to the study participants as part of the required study procedures; includes investigational drug(s), control(s) or background therapy
Study treatment discontinuation	When the subject permanently stops taking study treatment prior to the defined study treatment completion date
Subject	A trial participant (can be a healthy volunteer or a patient)
Subject number	A unique number assigned to each subject upon signing the informed consent. This number is the definitive, unique identifier for the subject and should be used to identify the subject throughout the study for all data collected, sample labels, etc.
Treatment number	A unique identifier assigned in non-randomized studies to each dosed subject, corresponding to a specific treatment arm
Variable	A measured value or assessed response that is determined in specific assessments and used in data analysis to evaluate the drug being tested in the study
Withdrawal of consent (WoC)	Withdrawal of consent from the study occurs only when a subject does not want to participate in the study any longer and does not allow any further collection of personal data

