### 8.1.1 Information to be collected on screening failures

Patients who sign an informed consent but fail to be started on treatment for any reason will be considered a screen failure.

The reason for the screening failure will be entered on the screening disposition page. If the patient fails to be randomized, the IRT must be notified within 2 days of the screen fail that the patient was not randomized.

Information on what data must collected for screening failures and further information on re-screening is outlined in the SOM.

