# 10.1.3 SAE reporting

To ensure subject safety, every SAE, regardless of causality, occurring after the subject has provided informed consent and until 30 days following the last administration of study treatment must be reported to Novartis safety immediately, without undue delay, but under no circumstances later than within 24 hours of obtaining knowledge of the events (Note: If more stringent, local regulations regarding reporting timelines prevail). Detailed instructions regarding the submission process and requirements are to be found in the investigator folder provided to each site.

- Screen Failures (e.g. a subject who is screened but is not treated or randomized): SAEs occurring after the subject has provided informed consent until the time the subject is deemed a Screen Failure must be reported to Novartis
- Baseline Failures (e.g. A subject who is screened but not randomized/treated after the baseline visit): SAEs collected between time subject signs ICF until time that subject is determined to be a baseline failure.
- Randomized OR Treated Subjects: SAEs collected between time subject signs ICF until 30 days after the subject has discontinued or stopped study treatment.

All follow-up information for the SAE including information on complications, progression of the initial SAE and recurrent episodes must be reported as follow-up to the original episode immediately, without undue delay, and under no circumstances later than 24 hours of the investigator receiving the follow-up information (Note: If more stringent, local regulations regarding reporting timelines prevail). An SAE occurring at a different time interval or otherwise considered completely unrelated to a previously reported one must be reported separately as a new event.

If the SAE is not previously documented in the Investigator's Brochure or Package Insert (new occurrence) and is thought to be related to the study treatment, a CMO & PS Department associate may urgently require further information from the investigator for health authority reporting. Novartis may need to issue an Investigator Notification (IN) to inform all investigators involved in any study with the same study treatment that this SAE has been reported.

Suspected Unexpected Serious Adverse Reactions (SUSARs) will be collected and reported to the competent authorities and relevant ethics committees in accordance with EU Guidance 2011/C 172/01 or as per national regulatory requirements in participating countries.

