1.4 Study design and treatment

This is a randomized, patient- and investigator-blinded, placebo-controlled, parallel-group study investigating the preliminary efficacy and safety of QBW251 administered orally for 12 weeks in participants with bronchiectasis. Approximately 72 participants will be randomized in a 1:1 ratio to receive either QBW251 300 mg b.i.d. or placebo in order to achieve 60 participants who complete the treatment period based on the assumption of a 16% dropout rate. The sample size assumptions will be reviewed in an interim analysis in a blinded manner when approximately 14 participants complete the treatment period.

The study consists of the following periods: Screening, baseline/Day 1, treatment period, and end of study assessments (EOS) visit followed by an additional post-treatment safety follow up via phone call. The total duration for each patient in the study is up to approximately 19 weeks.

The study design is described in Figure 3-1 below.

2 First interpretable results (FIR)

First interpretable results (FIR) will not be provided for this trial due to study termination.

3 Interim analyses

A blinded interim analysis is planned for this study when approximately 14 participants will complete Day 84 post treatment assessment. The purpose of this IA is to confirm sample size assumptions while assessing the variability in bacterial colonization of PPMs in this population. If the variability is larger than the variability assumed originally, a re-estimation/adjustment of the sample size may be applied for the rest of the study.

There will be no pause in enrollment at the time of interim analysis, and subjects may continue to be enrolled until the interim analysis is complete.

All enrolled subjects and the participating investigators will remain blinded during the entire study. Only the sponsor may be unblinded at the interim as necessary.

4 Analysis sets

For all analysis sets, subjects will be analyzed according to the study treatment(s) received.

No screen failure data will be presented.

The Safety Set includes all subjects who received at least one dose of study treatment. The safety set will be used in the analysis of all safety variables.

The PK analysis set will include all subjects with at least one available valid (i.e. not flagged for exclusion) PK concentration measurement, who received any study drug and with no protocol deviations that affect PK data. The PK serial sub-group set will include all subjects

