
with at least one evaluable drug concentration data sample and who consented to participate in the PK serial sub-group.

The PD analysis set will include all subjects with available PD data at both baseline and at least one post-baseline assessment that are not affected by any protocol deviations.

The analysis sets and protocol deviation codes are related as follows:

Table 4-1 Protocol deviation codes and analysis sets

	-	
Category Deviation code	Text description of deviation	Data exclusion
Subjects are exclu	ded from Safety analysis in case of these PDs:	Exclude subject from Safety analysis set
INCL01	Informed consent was not obtained before any assessment	Υ
Subjects are exclu	Exclude subject from PK analysis set	
INCL01	Informed consent was not obtained before any assessment	Y
OTH07	Patient received incorrect dose	Y
Subjects are exclu	ded from PD analysis in case of these PDs:	Exclude subject from PD analysis sets
INCL01	Informed consent was not obtained before any assessment	Υ

5 Statistical methods for Pharmacokinetic (PK) parameters

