7.2 Descriptive analyses

Categorical data will be presented as frequencies and percentages. For continuous data, mean, standard deviation, median, minimum, and maximum will be presented. Day 1 is defined as the date of first study drug administration. Study day is calculated relative to Day 1.

Subject demographics and other baseline characteristics

Demographic, including age, sex, race, ethnicity, and other baseline data including, baseline height, baseline weight, baseline BMI, past medical history including smoking history, history of bronchiectasis exacerbations and current medical conditions including allergies present

before signing the informed consent will be summarized descriptively by treatment group for the Safety set, if data allows.

BMI (kg/m^2) = Weight (kg) / [Height (m) * Height (m)]

All data for background and demographic variables will be listed by treatment group and subject. Summary statistics will be provided by treatment group. Continuous variables will be summarized using descriptive statistics (mean, SD, median, minimum and maximum) and categorical variables will be summarized in terms of the number and percentage of subjects in each category.

Medical history was coded using the Medical Dictionary for Regulatory Activities (MedDRA) terminology. History/conditions will be summarized for the safety analysis set, by primary system organ class and preferred term, and overall. Verbatim recorded history/conditions will be listed together with the coded terms, date of diagnosis/surgery and whether the problem was active at the time of first study drug dose.

Subject disposition

A disposition summary will be presented for all subjects in the safety analysis set. This table will present the number and percentage of subjects who randomized, completed and discontinued early, along with the reasons for early discontinuation.

The number and percentage of subjects in each analysis set will be summarized by treatment group. All analysis set results will be presented in listings by subject. A separate listing of all subjects excluded from any analysis set and the reasons for their exclusion will be provided.

All study completion data will be listed by subject.

Treatment

Data for study drug administration, rescue medication and concomitant therapies will be listed by treatment group and subject.

Summary statistics will be provided for the duration of exposure to study treatment using the safety analysis set.

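### SAP 7.2 counts the randomised and the early losses on the Safety Set, so patients randomised but never dosed, and dosed patients excluded under INCL01, drop out of the disposition table (minor)

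*SAP*

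**What the plan says.** SAP 7.2, under subject disposition, fixes the population: "A disposition summary will be presented for all subjects in the safety analysis set". It then fixes the content: "This table will present the number and percentage of subjects who randomized, completed and discontinued early, along with the reasons for early discontinuation". No other disposition table is planned.

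SAP section 4 defines the population: "The Safety Set includes all subjects who received at least one dose of study treatment". Table 4-1 then removes from it anyone with deviation INCL01, described as "Informed consent was not obtained before any assessment", whether or not that person was dosed. The SAP defines no set of all randomised subjects. Protocol 12.2 mentions a full analysis set, but neither Protocol 12.1 nor SAP section 4 defines one.

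Four parts of the protocol bear on the patient who is randomised and then not dosed:

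- Section 6.3.2 foresees the case. The IRT is told within 2 days and the reason is entered in the CRF.
- Section 8.1.1 says: "Patients who sign an informed consent but fail to be started on treatment for any reason will be considered a screen failure". It makes no exception for someone already randomised.
- The glossary defines a screen failure as "A subject who is screened but is not treated or randomized", which can be read either way for this patient.
- Section 10.1.3 lists screen failures separately from another group: "Randomized OR Treated Subjects: SAEs collected between time subject signs ICF until 30 days after the subject has discontinued". Section 9.2 likewise asks for a 30-day safety call for everyone randomised or treated.

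SAP section 4 also states: "No screen failure data will be presented".

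**The concern.** A table with a randomised row should be able to contain every randomised subject, and this one cannot. If a patient is allocated by the IRT and leaves before the first capsule, the table shows one fewer randomised and one fewer early loss, and nothing in the table signals the gap. A dosed patient excluded under INCL01 disappears in the same way, from whichever outcome row would have applied.

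What is at stake is the participant flow in the report. Attrition between allocation and first dose is the part a reader cannot reconstruct from a treated-only table. The trial was terminated, and the SAP itself cites a low sample size, so a single missing patient carries more weight than it would have at the planned size.

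The protocol wording adds a second difficulty. If a randomised, undosed patient is classed as a screen failure under the literal text of 8.1.1, the SAP rule against presenting screen-failure data could be taken to bar that patient from the listings too.

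**Working it through.** **The plan's own figures (Protocol 12.8.1).** Inputs: 60 completers, 30 per arm; 16% drop-out; difference 1.5 and SD 2.8 on the log10 scale; 10% significance level.

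- Randomised number: 60 / (1 − 0.16) = 71.4, rounded up to 72. This matches.
- Power, one-sided at 10%: 1.5 / (2.8 × √(2/30)) = 2.075; 2.075 − 1.282 = 0.793; Φ(0.793) = 0.786. This agrees with the stated 79% to within a point. A two-sided 10% test gives 0.666 and does not match.

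Neither figure depends on the denominator of the disposition table, so nothing below alters them.

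**Who is in the table.** Setting SAP 7.2, SAP section 4 and Table 4-1 side by side:

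| Patient | In Safety Set? | Effect on the table |
|---|---|---|
| Randomised, dosed, completed | Yes | Counted correctly |
| Randomised, dosed, stopped early | Yes | Counted correctly, with reason |
| Randomised, never dosed | No | Missing from randomised and early-loss counts |
| Randomised, dosed, INCL01 | No | Missing from randomised count and from the completed or early-loss count |

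**Size, never-dosed patients (illustration).** Take the planned 72 randomised and 60 completers, hence 72 − 60 = 12 losses. Let k of the 12 occur before the first dose. The documents give no value for k, so a range is shown. On all randomised subjects the rate is 12/72 = 16.7% whatever k is. On the Safety Set it is (12 − k)/(72 − k):

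| k (assumed) | Shown as randomised | Shown as discontinued | Rate |
|---|---|---|---|
| 0 | 72 | 12 | 16.7% |
| 1 | 71 | 11 | 15.5% |
| 3 | 69 | 9 | 13.0% |
| 6 | 66 | 6 | 9.1% |

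**Size, INCL01.** One dosed INCL01 patient who stopped early has the same effect as k = 1. One who completed moves the rate slightly the other way, to 12/71 = 16.9%.

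**Smaller trial.** Each omitted patient is 1/N of those randomised: 1/72 = 1.4% at the planned size and, for an assumed N of 30, 1/30 = 3.3%. The documents do not give the final number randomised.

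**The case against.** The strongest case on the other side has four parts.

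1. **Most losses are still shown.** A reader might infer that the table omits post-randomisation losses generally, or that losses cannot be compared between arms. The documents do not support this. Every discontinuation after the first dose stays in the table with its reason, and SAP section 7 has tables presented by treatment group. Only losses before the first dose, and INCL01 exclusions, fall out. This part stands in full.

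2. **Other outputs help.** SAP 7.2 also plans analysis-set counts by treatment group, a listing of subjects excluded from any analysis set with reasons, and a listing of study completion data. INCL01 patients belong in the exclusion listing by definition, and never-dosed patients may appear there. This stands as mitigation. However, the denominator of the analysis-set percentages is not stated, the listing may conflict with the no-screen-failure rule, and a listing does not correct counts in a summary table.

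3. **The screen-failure label is not settled.** A reader might infer that every randomised, undosed patient is reclassified as a screen failure. That follows from one sentence of 8.1.1 read alone. The rest of that section links screen failure to not being randomised. Sections 6.3.2, 9.2 and 10.1.3 treat randomised patients separately, and the glossary is ambiguous. What stands is an inconsistency between sections, not an established relabelling.

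4. **The count may be zero.** Randomisation follows completed baseline assessments and reconfirmed eligibility, and the first dose is planned in the clinic on the same day (Protocol 3.1). With no such patients and no INCL01 exclusions, the two versions of the table agree. This also stands. But the report shows the count to be zero only if its table starts from all randomised subjects.

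**Conclusion.** The point holds, at minor severity. As written, the disposition table in SAP 7.2 miscounts the randomised whenever a patient is randomised but not dosed, or is dosed and then excluded under INCL01. It also miscounts early losses whenever such a patient did not complete.

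It would go too far to say that the reported figures will be wrong. That depends on whether such patients exist, which the documents do not say. The rates shown above rest on assumed values of k and, for the smaller trial, an assumed N. Early discontinuation among treated patients is itself a legitimate quantity, and its population is stated openly; the fault is in using that population for a count of the randomised.

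No efficacy result, sample size or power figure is affected. The separate inconsistency about the status of the randomised, undosed patient also reaches SAE collection under Protocol 10.1.3. Those passages must be reconciled, and this review does not say which follow-up rule should prevail.

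**What to change.** **In the SAP.** Base the disposition table on all randomised subjects, by randomised arm. Add a row for randomised but not treated, with reasons, and a row for INCL01 exclusions; keep the completed and discontinued-early rows with reasons. State that, for the SAP, a screen failure is a patient who was not randomised, so that the no-screen-failure rule cannot remove a randomised patient from the tables or listings.

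The cost is a sentence or two and one changed table shell. No new data are needed: randomisation data already reach the sponsor from the IRT (Protocol 11.2), and the reason for non-treatment is already entered in the CRF (Protocol 6.3.2).

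**In the protocol.** Reconcile 8.1.1 with 6.3.2, 9.2 and 10.1.3 on the status of randomised, undosed patients. Under Protocol 14.1 this needs a written amendment with the approvals listed there, which is not a trivial step for a terminated study. It can wait for the next opportunity, and the SAP change does not depend on it.
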